10.3.2 Definition of SAE

An SAE is defined as any adverse event that, at any dose:

a. Results in death

b. Is life-threatening

The term 'life-threatening' in the definition of 'serious' refers to an event in which the participant was at risk of death at the time of the event. It does not refer to an event, which hypothetically might have caused death, if it were more severe.

c. Requires inpatient hospitalization or prolongation of existing hospitalization

- In general, hospitalization signifies that the participant has been admitted (usually involving at least an overnight stay) at the hospital or emergency ward for observation and/or treatment that would not have been appropriate in the physician's office or outpatient setting. Complications that occur during hospitalization are AEs. If a complication prolongs hospitalization or fulfills any other serious criteria, the event is serious. When in doubt as to whether "hospitalization" occurred or was necessary, the AE should be considered serious.
- Hospitalization for elective treatment of a pre-existing condition that did not worsen from baseline is not considered an AE.

d. Results in persistent or significant disability/incapacity

- The term disability means a substantial disruption of a person's ability to conduct normal life functions.
- This definition is not intended to include experiences of relatively minor medical significance such as uncomplicated headache, nausea, vomiting, diarrhea, influenza, and accidental trauma (eg, sprained ankle) which may interfere with or prevent everyday life functions but do not constitute a substantial disruption.

e. Is a congenital anomaly/birth defect

f. Is other medically important event

- The term "Other medically important events" refers to events which do not meet any of the above seriousness criteria, but which are considered as serious based on Investigator medical judgment
- Medical or scientific judgment should be exercised by the Investigator in deciding whether
 expedited reporting is appropriate in other situations such as significant medical events that
 may not be immediately life-threatening or result in death or hospitalization but may

- jeopardize the health of the participant or may require intervention to prevent one of the other outcomes listed in the above definition. These important medical events should also usually be considered serious.
- Examples of such events include invasive or malignant cancers, intensive treatment in an
 emergency room or at home for allergic bronchospasm, blood dyscrasias or convulsions or
 development of intervention dependency or intervention abuse, new onset diabetes or
 autoimmune disease or suspected transmission of any infectious agent via an authorised
 medicinal product.

Note: Serious and severe are not synonymous. The term severe is often used to describe the intensity of a specific event as corresponding to Grade 3. This is not the same as serious, which is based on participant / event outcome or action criteria usually associated with events that pose a threat to a participant's life or functioning.

10.3.3 Recording and Follow-Up of AE and/or SAE

AE and SAE Recording

- When an AE/SAE occurs, it is the responsibility of the Investigator to review all documentation (eg, hospital progress notes, laboratory reports, and diagnostics reports) related to the event.
- The Investigator will then record all relevant AE/SAE information.
- It is not acceptable for the Investigator to send photocopies of the participant's medical records to the Sponsor in lieu of completion of the CRF pages.
- There may be instances when copies of medical records for certain cases are requested by the Sponsor. In this case, all participant identifiers, with the exception of the participant number, will be redacted on the copies of the medical records before submission to the Sponsor.
- The Investigator will attempt to establish a diagnosis of the event based on signs, symptoms, and/or other clinical information. Whenever possible, the diagnosis (not the individual signs/symptoms) will be documented as the AE/SAE.

Assessment of Causal Relationship

By convention, all AEs reported at the injection site (either solicited or unsolicited) and all solicited systemic AEs are considered to be related to the IMP (see definition in Section 6) and therefore are referred to as reactions and do not require the Investigator's opinion on relatedness.

- Causal relationship of unsolicited systemic AEs and SAEs will be recorded as follows:
 - For non-serious unsolicited systemic AEs (except for non-serious AESIs), relationship to study intervention will usually be assessed by the Investigator only.

- For SAEs and non-serious AESIs, relationship to study intervention will be assessed by both the Investigator and the Sponsor (except for injection site reactions which will be related by default). Sponsor assessment is entered in the GPV database only.
- For SAEs only, the causal relationship to study procedures (related/not related to study procedures) will be assessed by both the Investigator and the Sponsor. Sponsor assessment is entered in the GPV database only.
- The Investigator will assess the causal relationship between each unsolicited systemic AE and the study intervention administered as either not related or related, based on the following definitions:
 - Not related The AE is clearly / most probably caused by other etiologies such as participant's underlying condition, therapeutic intervention, or concomitant therapy; or the delay between vaccination and the onset of the AE is incompatible with a causal relationship; or the AE started before vaccination (screening phase, if applicable)
 - Related There is a "reasonable possibility" that the AE was caused by the study intervention administered, meaning that there are facts (evidence) or arguments to suggest a causal relationship
- The Investigator will use clinical judgment to determine the relationship.
- Alternative causes, such as underlying disease(s), concomitant therapy, and other risk factors, as well as the temporal relationship of the event to study intervention administration will be considered and investigated.
- The Investigator will also consult the IB and/or Product Information, for marketed products, in his/her assessment.
- For each AE/SAE, the Investigator must document in the medical notes that he/she has reviewed the AE/SAE and has provided an assessment of causal relationship.
- There may be situations in which an SAE has occurred, and the Investigator has minimal information to include in the initial report to the Sponsor. However, it is very important that the Investigator always makes an assessment of causal relationship for every event before the initial transmission of the SAE data to the Sponsor.
- The Investigator may change his/her opinion of causal relationship in light of follow-up information and send an SAE follow-up report with the updated causal relationship assessment.
- The causal relationship assessment is one of the criteria used when determining regulatory reporting requirements.

Follow-up of AEs and SAEs

• The Investigator is obligated to perform or arrange for the conduct of supplemental measurements and/or evaluations as medically indicated or as requested by the Sponsor to elucidate the nature and/or causal relationship of the AE or SAE as fully as possible. This

- may include additional laboratory tests or investigations, histopathological examinations, or consultation with other health care professionals.
- If a participant dies during participation in the study or during a recognized follow-up period, when available the Investigator will provide the Sponsor with a copy of any post-mortem findings including histopathology.
- New or updated information will be recorded in the originally submitted documents.
- The Investigator will submit any updated SAE data to the Sponsor within 24 hours of receipt of the information.
- Serious adverse events likely to be related to the study intervention, that persist at the end of the study will be followed up by the Investigator until their complete disappearance or the stabilization of the participant's condition. The Investigator will inform the Sponsor of the date of final disappearance of the event or the date of "chronicity" establishment.

10.3.4 Reporting of SAEs

SAE Reporting to the Sponsor via an Electronic Data Collection Tool

- The primary mechanism for reporting an SAE to the Sponsor will be the electronic data collection tool.
- If the electronic system is unavailable, then the site will use the paper SAE data collection tool (see next section) to report the event within 24 hours. The site will enter the SAE data into the electronic system as soon as it becomes available.
- After the study is completed at a given site, the electronic data collection tool will be taken off-line to prevent the entry of new data or changes to existing data.
- If a site receives a report of a new SAE from a study participant or receives updated data on a previously reported SAE after the electronic data collection tool has been taken off-line, then the site can report this information on a paper SAE form (see next section).
- Details regarding SAE reporting can be found in the Operating Guidelines.

SAE Reporting to the Sponsor via Paper CRF

- The SAE paper CRF can be sent to the Sponsor by one of the following means:
 - By fax, to the following number:
 - In PDF format to the following e-mail address, using a method of transmission that includes password protection:
 - By express mail, to the following address: Global Pharmacovigilance, Sanofi Pasteur SA, [name]

Safety Emergency Call

If, as per the Investigator's judgment, a participant experiences a medical emergency, the Investigator may contact the Sponsor's RMO for advice on how to address any study-related medical question or problem. If the RMO is not available, then the Investigator may contact the Call Center—available 24 hours a day, 7 days a week—that will forward all safety emergency calls to the appropriate primary or back-up Sanofi Pasteur contact, as needed. The toll-free contact information for the Call Center is provided in the Operating Guidelines.

This process does not replace the need to report an SAE. The Investigator is still required to follow the protocol-defined process for reporting SAEs to the GPV Department.

In case of emergency code-breaking, the Investigator is required to follow the code-breaking procedures described in Section 6.3.2.

10.3.5 Assessment of Intensity

The Investigator will make an assessment of intensity for each AE reported during the study. An intensity grade will be assigned to each AE. The intensity grading scales used in this study are adapted from the "FDA Guidance for Industry: Toxicity Grading Scale for Healthy Adult and Adolescent Volunteers Enrolled in Preventive Vaccine Clinical Trials, September 2007".

10.3.5.1 Tables for Clinical Abnormalities

10.3.5.1.1 Solicited AR Intensity Grading Scale

Table 10.1: Solicited injection site reactions: terminology, definitions, and intensity scales

CRF term (MedDRA lowest level term [LLT])	Injection site pain	Injection site erythema	Injection site swelling
Diary card term	Pain	Redness	Swelling
Definition	Pain either present spontaneously or when the injection site is touched or injected limb is mobilized	Presence of a redness including the approximate point of needle entry	Swelling at or near the injection site Swelling or edema is caused by a fluid infiltration in tissue or cavity and, depending on the space available for the fluid to disperse, swelling may be either soft (typically) or firm (less typical) to touch and thus can be best described by looking at the size of the swelling
Intensity scale*	CRF:	Grade 1: \geq 25 to	Grade 1: \geq 25 to \leq 50 mm
	Grade 1: A type of adverse event that is usually transient and may require only minimal treatment or therapeutic intervention. The event does not generally interfere with usual activities of daily living. Grade 2: A type of adverse event that is usually alleviated with additional therapeutic intervention. The event interferes with usual activities of daily living, causing discomfort but poses no significant or permanent risk of harm to the research participant. Grade 3: A type of adverse event that interrupts usual activities of daily living, or significantly affects clinical status, or may require intensive therapeutic intervention. Diary card: Grade 1: No interference with usual activities Grade 2: Some interference with usual activities Grade 3: Significant; prevents usual activities	\leq 50 mm Grade 2: \geq 51 to \leq 100 mm Grade 3: $>$ 100 mm	Grade 2: ≥ 51 to ≤ 100 mm Grade 3: > 100 mm

MedDRA: Medical Dictionary for Regulatory Activities

^{*} For the scale will be provided in the CRF and the intensity will be transcribed from in the diary card. For other injection site reactions (erythema and swelling), the classification as Grades 1, 2, or 3 will be applied at the time of statistical analysis; the scale is provided for information purposes only. The actual size of the reaction will be reported in the CRF.

Table 10.2: Solicited systemic reactions: terminology, definitions, and intensity scales

CRB term (MedDRA lowest level term [LLT])	Fever	Headache	Malaise	Myalgia
Diary card term	Temperature	Headache	Feeling unwell	Muscle aches and pains
Definition	Elevation of temperature to ≥°38.0°C (≥ 100.4°F)	Pain or discomfort in the head or scalp. Does not include migraine.	General ill feeling. Malaise is a generalized feeling of discomfort, illness, or lack of wellbeing that can be associated with a disease state. It can be accompanied by a sensation of exhaustion or inadequate energy to accomplish usual activities.	Muscle aches and pains are common and can involve more than one muscle at the same time. Muscle pain can also involve the soft tissues that surround muscles. These structures, which are often referred to as connective tissues, include ligaments, tendons, and fascia (thick bands of tendons). Does not apply to muscle pain at the injection site which should be reported as injection site pain.
Intensity scale*	Grade 1: $\geq 38.0^{\circ}$ C to $\leq 38.4^{\circ}$ C,	CRB:	CRB:	CRB:
	or ≥ 100.4°F to ≤ 101.1°F	Grade 1: A type of adverse event that is usually transient and may require only minimal treatment or therapeutic intervention. The event does not generally interfere with usual activities of daily living.	Grade 1: A type of adverse event that is usually transient and may require only minimal treatment or therapeutic intervention. The event does not generally interfere with usual activities of daily living.	Grade 1: A type of adverse event that is usually transient and may require only minimal treatment or therapeutic intervention. The event does not generally interfere with usual activities of daily living.

Grade $2: \ge 38.5^{\circ}\text{C}$ to $\le 38.9^{\circ}\text{C}$, or $\ge 101.2^{\circ}\text{F}$ to $\le 102.0^{\circ}\text{F}$	Grade 2: A type of adverse event that is usually alleviated with additional therapeutic intervention. The event interferes with usual activities of daily living, causing discomfort but poses no significant or permanent risk of harm to the research participant.	Grade 2: A type of adverse event that is usually alleviated with additional therapeutic intervention. The event interferes with usual activities of daily living, causing discomfort but poses no significant or permanent risk of harm to the research participant.	Grade 2: A type of adverse event that is usually alleviated with additional therapeutic intervention. The event interferes with usual activities of daily living, causing discomfort but poses no significant or permanent risk of harm to the research participant.
Grade $3: \ge 39.0$ °C or ≥ 102.1 °F	Grade 3: A type of adverse event that interrupts usual activities of daily living, or significantly affects clinical status, or may require intensive therapeutic intervention.	Grade 3: A type of adverse event that interrupts usual activities of daily living, or significantly affects clinical status, or may require intensive therapeutic intervention.	Grade 3: A type of adverse event that interrupts usual activities of daily living, or significantly affects clinical status, or may require intensive therapeutic intervention.
	Diary card: Grade 1: No interference with usual activities	Diary card: Grade 1: No interference with usual activities	Diary card: Grade 1: No interference with usual activities
	Grade 2: Some interference with usual activities Grade 3: Significant; prevents usual activities	Grade 2: Some interference with usual activities Grade 3: Significant; prevents usual activities	Grade 2: Some interference with usual activities Grade 3: Significant; prevents usual activities

MedDRA: Medical Dictionary for Regulatory Activities

^{*} For all reactions (except fever), the scale will be provided in the CRF and the intensity will be transcribed from the diary card. For fever, will be recorded will be recorded, and the classification as Grade 1, 2, or 3 will be assigned at the time of the statistical analysis based on the unit used to measure the temperature and the intensity scale.

Important notes for the accurate assessment of temperature:

Participants are to measure body temperature once per day, preferably always at the same time. The optimal time for measurement is the evening, when body temperature is the highest. Temperature is also to be measured at the time of any apparent fever. The observed daily temperature and the route of measurement are to be recorded in the DC and the highest temperature will be recorded by the site in the CRF. The preferred route for this study is oral.

10.3.5.1.2 Unsolicited AE Intensity Grading Scale

For measurable unsolicited AEs that are part of the list of solicited reactions, the corresponding scale for solicited reactions will be used (see Section 10.3.5.1.1).

All other unsolicited AEs will be classified according to the following intensity scale:

- Grade 1
 - CRF: A type of adverse event that is usually transient and may require only minimal treatment or therapeutic intervention. The event does not generally interfere with usual activities of daily living.
 - Diary card: No interference with usual activities.
- Grade 2
 - CRF: A type of adverse event that is usually alleviated with additional therapeutic intervention. The event interferes with usual activities of daily living, causing discomfort but poses no significant or permanent risk of harm to the research participant.
 - Diary card: Some interference with usual activities.
- Grade 3
 - CRF: A type of adverse event that interrupts usual activities of daily living, or significantly affects clinical status, or may require intensive therapeutic intervention.
 - Diary card: Significant; prevents usual activities.

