4.2.2.1.1 Daily Intensity

All daily records for solicited reactions will be derived into daily intensity according to the following classification: None, Grade 1, Grade 2, Grade 3, or Missing (Unknown).

For measurable injection site reactions:

- None: > 0 to < 25 mm
- Grade $1: \ge 25$ to ≤ 50 mm
- Grade $2: \ge 51$ to ≤ 100 mm
- Grade 3: > 100 mm

For Fever:

- None: $< 38.0^{\circ}$ C or $< 100.4^{\circ}$ F
- Grade $1: \ge 38.0^{\circ}$ C to $\le 38.4^{\circ}$ C or $\ge 100.4^{\circ}$ F to $\le 101.1^{\circ}$ F
- Grade 2: \geq 38.5°C to \leq 38.9°C or \geq 101.2°F to \leq 102.0°F
- Grade $3: \ge 39.0^{\circ}$ C or $\ge 102.1^{\circ}$ F

For the derivation of daily intensities, the following sequential steps will be applied:

- 1) Solicited reactions (except Fever/Pyrexia) with CRF presence recorded as "No" and with all daily records missing (Unknown) then all daily intensities will be derived as None.
- 2) For non-measurable solicited reactions, daily intensities will correspond to daily records reported in the clinical database. For measurable solicited reactions the daily measurements reported in the clinical database will be converted based upon the intensity scales defined in the protocol; this assumes a reaction that is too large to measure (non-measurable, "NM") is Grade 3. Note the intensity could be considered "None" (not a reaction) in the analysis despite being considered a reaction by the investigator (eg, swelling measurement > 0 mm but < 25 mm in adults).

Note: The maximum intensity on the ongoing period is derived from the record of the maximum intensity/measurement after the end of the solicited period following the rule described above.

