4.2.2.2 Unsolicited AEs

4.2.2.2.1 **Presence**

An observation will be considered an event if it has at least a verbatim term and is not a Grade 0 intensity event.

Grade 0 events will be not included in safety analysis but will be included in separate listings.

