4.2.2.2.2 Intensity

Intensity will be derived according to the following classification: None, Grade 1, Grade 2, Grade 3, or Missing.

If the unsolicited AE is measurable and its preferred term is part of the list of solicited reactions, then the measurement is derived based upon and following the same rule of the intensity scales defined in the protocol for that measurable injection site or systemic reaction. Note the intensity could be considered as "None" (not a reaction) in the analysis despite being considered a reaction by the investigator (eg, swelling measurement > 0 mm but < 25 mm in adults).

Intensity for the other unsolicited AEs will correspond to the value reported in the CRF.

The maximum intensity corresponds to the highest intensity for a unique term.

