4.2.2.3 Medically-Attended Adverse Event

An event will be considered as an MAAE if "Yes" is checked for "Is the event an MAAE?" in the CRF.

MAAE will be analyzed during the following time periods:

- Within 28 days after a vaccination
- During the period from 29 days after the vaccination up to M6 post-vaccination as part of the SAE (Serious MAAE) and at any time during the study as part of SAEs that are related or fatal (serious related or fatal MAAE)

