4.2.2.4 SAEs

An event will be considered as a serious event if "Yes" is checked for "Serious" in the CRF.

SAEs will be analyzed throughout the study using the following periods:

- Within 28 days after a vaccination
- During the period from 29 days after the vaccination until the last participant contact at M6
- During the study for related SAEs (ie, all related SAEs occurred during the study)

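### The SAP's Grade 0 exclusion for unsolicited AEs has no exception for flagged events, so a late injection-site reaction under 25 mm can drop out of AE, AR and possibly MAAE or SAE counts

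*Protocol*

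**What the plan says.** **Scale.** Protocol 10.3.5.1.2 sets the rule for unsolicited events: "For measurable unsolicited AEs that are part of the list of solicited reactions, the corresponding scale for solicited reactions will be used". SAP 4.2.2.2.2 applies it when the AE is measurable and its preferred term is on the solicited list; "then the measurement is derived based upon and following the same rule of the intensity scales defined in the protocol". All other unsolicited AEs keep the intensity recorded in the CRF.

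**Classes.** SAP 4.2.2.2.2: "Intensity will be derived according to the following classification: None, Grade 1, Grade 2, Grade 3, or Missing". Its note accepts that a reported event may come out as 'None', in its words "not a reaction) in the analysis despite being considered a reaction by the investigator", and gives swelling above 0 but under 25 mm as the example. The cut-off comes from SAP 4.2.2.1.1: "None: > 0 to < 25 mm". The same section treats a temperature below 38.0°C as 'None'.

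**Exclusion.** SAP 4.2.2.2.1 counts an observation as an event only if it has a verbatim term and is not Grade 0. It then says: "Grade 0 events will be not included in safety analysis but will be included in separate listings".

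**Flagged events.** SAP 4.2.2.3 begins "An event will be considered as an MAAE if" and SAP 4.2.2.4 begins "An event will be considered as a serious event if"; each goes on to name a CRF box and sets no grade condition. SAP 4.2.2 defines an SAE by the Investigator's judgement, reconciled with the pharmacovigilance database. SAP 4.2.2.7.3 has seriousness summarized as collected, with no derivation.

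**Discontinuation.** SAP 4.2.2.7.6 counts an unsolicited AE that caused discontinuation only if it is Grade 1 or higher, or of missing grade. For the disposition and safety overview tables it also counts a participant whose completion form is marked as ending for an adverse event.

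**The concern.** The 25 mm and 38.0°C cut-offs come from the diary-based reactogenicity scale. Applying them to unsolicited events lets a size measurement decide whether something the Investigator reported is an event at all. Seriousness, medical attendance and leaving the study do not depend on size. Protocol 10.3.2 itself separates serious from severe.

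The sound example is an injection-site reaction that starts after the solicited window closes on D08, measures under 25 mm, and leads the participant to seek medical advice. Protocol Table 10.1 sets no minimum size in its definitions of erythema and swelling. Protocol 10.3.1 treats unsolicited events at the injection site as related by default, and SAP 4.2.2 analyses them as adverse reactions. Such an event therefore meets the AE, AR and MAAE definitions, yet it can disappear from the tabulated counts. The same events could then be counted in one table and absent from another, and two programmers could produce different MAAE or SAE rows from the same SAP.

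**Working it through.** The plan states no figure to reproduce. The check traces one event through the rules.

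**1. Terms affected.** In Protocol Tables 10.1 and 10.2, the reactions graded by measurement are injection-site erythema, injection-site swelling and fever. Pain, headache, malaise and myalgia are graded by description and are not affected.

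**2. Cut-offs (SAP 4.2.2.1.1).** 1 mm and 24 mm give 'None'; 25 mm gives Grade 1. 37.5°C and 37.9°C give 'None'; 38.0°C gives Grade 1.

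**3. Link between the two rules.** SAP 4.2.2.2.2 yields 'None' and lists no Grade 0. SAP 4.2.2.2.1 excludes Grade 0 and does not mention 'None'. The exclusion reaches these events only if the two are equated. That is the natural reading, but it is an inference.

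**4. Trace.** Take an unsolicited injection-site swelling of 20 mm with derived intensity 'None', read as Grade 0:

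| Output | Result | Deciding rule |
|---|---|---|
| Unsolicited AE and AR counts | Excluded | SAP 4.2.2.2.1 |
| Separate listing | Included | SAP 4.2.2.2.1 |
| MAAE row, if flagged | Not settled | Excluded if 4.2.2.2.1 governs; included if 4.2.2.3 governs |
| SAE row, if flagged | Not settled | Excluded if 4.2.2.2.1 governs; included if 4.2.2.4 and 4.2.2.7.3 govern |
| SOC/PT discontinuation table | Excluded | Grade condition in 4.2.2.7.6 |
| Overview discontinuation row | Included only if the completion form says adverse event | 4.2.2.7.6 |
| Disposition table | Included only if the completion form says adverse event | 4.2.2.7.6 |

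The MAAE and SAE rows are unsettled because 4.2.2.3 and 4.2.2.4 classify an 'event', and 4.2.2.2.1 is where the SAP says which unsolicited observations are events. Nothing states which section takes precedence. The footnotes to the safety overview shell (SAP Table 7.8) do not settle it.

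In the last three rows, a participant who left because of this reaction can appear in two tables with no matching entry in the SOC/PT table.

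**5. Size of one omission, at the planned group sizes.**
- One participant is 1/380 = 0.26% in vYF and 1/190 = 0.53% in YF-VAX.
- Exact 95% upper limit for zero events is 1 − 0.025^(1/n): 0.97% for n = 380 and 1.92% for n = 190.
- Exact 95% upper limit for one event: about 1.46% for n = 380 and about 2.90% for n = 190.

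These figures show what losing any single event does to a row. They do not estimate how many events would be lost, and the documents give no figure for that.

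**The case against.** A reader might infer that the SAP deletes serious, medically attended or discontinuation events from all safety analyses. The documents do not support that, for four reasons.

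- The excluded observations stay in separate listings.
- SAP 4.2.2.7.6 still counts the participant in the disposition and overview tables through the completion form, whatever the AE grade.
- The MAAE, SAE and AESI rules sit in their own sections, rest on the Investigator's CRF box and carry no grade condition. SAEs are also reconciled with pharmacovigilance, and seriousness is taken as collected. Loss from those rows is one reading, not a stated outcome.
- The SAP never says that 'None' is Grade 0.

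The reach is also narrow. None of the three measurable terms is one of the AESI categories in Protocol 8.3.6, so AESI exposure is essentially nil. A temperature below 38.0°C does not meet the definition of fever in Protocol Table 10.2, so a low-temperature example carries little weight. Protocol 10.3.3 asks for the diagnosis rather than individual signs where possible, so a febrile hospitalisation would usually be recorded under another term and graded from the CRF. An AE with missing intensity is not Grade 0 and is kept. Safety is descriptive, and the rule is the same in both arms. The protocol's choice of scale is not itself an error; the exclusion comes from the SAP.

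All of this stands and limits the point. It leaves untouched the late injection-site reaction under 25 mm that is medically attended or causes discontinuation. It also leaves the undefined term, the missing exception, and the grade filter in SAP 4.2.2.7.6. That filter shows the SAP does let derived intensity override an Investigator's flag in at least one table.

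**Conclusion.** The point holds in a limited form and is minor. Taking 'None' as Grade 0, SAP 4.2.2.2.1 and 4.2.2.2.2 together remove sub-threshold measurable unsolicited AEs from the AE and AR counts, with no exception for flagged events. Whether they also leave the MAAE and SAE rows depends on which section governs, and the SAP does not say. The SOC/PT discontinuation table does exclude them, so it may not reconcile with the disposition and overview tables.

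The number of affected events is probably zero to a few; that is a judgement, since the documents give no rate. The effect runs in one direction only: it can lower counts but not raise them. The primary immunogenicity comparison is not touched. Excluding unflagged sub-threshold events from the tables is consistent with how solicited reactions are handled and is not criticised here.

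**What to change.** In SAP 4.2.2.2.1:
- Define Grade 0 as a derived intensity of 'None'.
- Limit the exclusion to unsolicited AEs not flagged as serious, AESI, MAAE or causing discontinuation.
- State that flagged events are analysed whatever their derived intensity, with intensity shown as 'below Grade 1'.

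In SAP 4.2.2.7.6, change the grade condition for unsolicited AEs to match, so that the SOC/PT, overview and disposition tables can be reconciled.

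The cost is a few sentences and one programming condition, with no change to design or data collection. The downside is that reported SAE, MAAE or discontinuation counts may be slightly higher.
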